8.1.5.2. Incomplete Dates

If the onset date of the AE is incomplete and the AE stop date is not prior to the first dosing date of study drug, then the month and year (or year alone if month is not recorded) of onset determine whether an AE is treatment emergent. For the double-blind phase, the event is considered treatment emergent if both of the following 2 criteria are met:

- The AE onset is the same as or after the month and year (or year) of the first dosing date of double-blind study drug, and
- The AE onset date is the same as or before the month and year (or year) of the extension phase open-label filgotinib or extension phase start date (if non-missing) or before the date corresponding to 30 days after the date of the last dose of double-blind study drug (if permanently discontinued from double-blind study drug)

For the extension phase, the event is considered treatment emergent if both of the following 2 criteria are met:

- The AE onset is the same as or after the month and year (or year) of the first dosing date of open-label filgotinib/start date in the extension phase, and
- The AE onset date is the same as or before the month and year (or year) corresponding to 30 days after the date of the last dose of open-label filgotinib/last date in extension phase (if permanently discontinued from extension phase drug or entered monitoring phase for meeting a pre-specified sperm decrease threshold) or all events after first dose date of drug for extension phase if subject is ongoing in extension phase at time of interim analysis

An AE with completely missing onset and stop dates, or with the onset date missing and a stop date later than the first dosing date of double-blind study drug, will be considered to be treatment emergent for the double-blind phase. In addition, an AE with the onset date missing and incomplete stop date with the same or later month and year (or year alone if month is not recorded) as the first dosing date of open-label filgotinib/first date in extension phase will be considered treatment emergent for extension phase.

8.1.5.3. Analysis of Exposure-Adjusted Incidence Rate

The Exposure-Adjusted Incidence Rate (EAIR) for a TEAE is defined as:

$$\text{Incidence rate per 100 patient years of exposure (PYE)} \\ = \frac{\text{Total number of subjects with an event}}{\text{Total PYE}} \times 100.$$

The total patient-years of exposure (PYE) to a treatment is the sum of the individual subject's PYE and is defined as:

For subjects with an event:

$$\text{PYE} = (\text{Event start date} - \text{first date in DB phase} + 1) / 365.25$$

For subjects with no event:

$$\text{PYE} = (\text{Calculation end date} - \text{first date in DB phase} + 1) / 365.25$$

where calculation end date for the double blind phase = the earliest date among

(last dosing date of double blind phase +30, first date in extension phase of the study -1 day, death date, cutoff date). If the last study drug dosing date is missing and the subject has stopped drug, the latest date among study drug end date, clinical visit date, and laboratory sample collection date that occurred during the double-blind phase will be used.

where calculation end date for the entire study display = the earliest date among

(last dosing date of OL filgotinib+ 30 days [subjects in the filgotinib to OL filgotinib sequence who permanently discontinued OL filgotinib]; last dosing date of double-blind filgotinib [subjects in the filgotinib to standard of care group], last date on standard of care in extension phase [subjects in placebo to standard of care sequence who switched to monitoring phase or early terminated from study after starting extension phase], last dosing date of double-blind study drug + 30 for subjects who did not start extension phase, data cutoff date, death date).

If event start date during the double-blind phase is partially missing and the non-missing portion matches the first dosing date (month and/or year) of double-blind study drug; or if the date is completely missing, AE onset is imputed as the date of first dose of double-blind study drug. Otherwise it is imputed as the first day of the month (if only day is missing) or January 1st of the year (if day and month are missing).

The exact 95% CI based on the Poisson distribution [{Ulm 1990}](#) for EAIR is defined as:

$$\left(\frac{\chi^2_{2(\text{Total number of subjects with an event}), 0.025}}{2 \times \text{Total PYE}}, \frac{\chi^2_{2(1+\text{Total number of subjects with an event}), 0.975}}{2 \times \text{Total PYE}} \right) \times 100.$$

To estimate the 95% CI for the EAIR difference between two treatment groups for events during the double-blind phase, the Method of Variance Estimates Recovery (MOVER)-type confidence interval described in [{Li 2011}](#) will be used:

$$L = \frac{n_a}{T_a} - \frac{n_b}{T_b} - \sqrt{\left(\frac{n_a}{T_a} - l_a\right)^2 + \left(u_b - \frac{n_b}{T_b}\right)^2}, \quad U = \frac{n_a}{T_a} - \frac{n_b}{T_b} + \sqrt{\left(u_a - \frac{n_a}{T_a}\right)^2 + \left(\frac{n_b}{T_b} - l_b\right)^2},$$

Where n_a is the total number of subjects with the event, T_a is the total PYE, l_a is the lower bound and u_a is the upper bound of the exact 95% CI based on the Poisson distribution for group a. Similarly for group b.

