Study Drug	Study drug is defined as blinded filgotinib or placebo during the Double-blind Treatment Phase and open-label filgotinib during the Extension Phase.
First unblinded interim analysis (IA1)	Unblinded Week 26 analysis to be performed after at least 200 evaluable subjects pooled across studies GS-US-418-4279 (GLPG0634-CL-228) and GLPG0634-CL-227 complete Week 13 and evaluable subjects from Study GLPG0634-CL-227 complete Week 26 or permanently discontinue from study drug. Referred to as 'Week 26 Analysis' in the SAP.
Second unblinded interim analysis (IA2)	Unblinded Week 26 analysis to be performed after all subjects reach Week 26 and all subjects with a $\geq 50\%$ decrease in sperm concentration, and/or motility, and/or morphology up to Week 26 enter the Monitoring Phase and either meet reversibility criteria or are followed off-treatment for 52 weeks, whichever occurs first. Referred to as 'Week 26 and Reversibility Analysis for Pre-specified Sperm Decreases Up to Week 26' in the SAP.

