#### **8.5.4. Other Safety Analysis**

All other safety analyses will be performed using the Safety Analysis Set.

Safety will be evaluated by assessment of clinical laboratory tests, PEs, ECG and vital signs measurements at various time points during the study, and by the documentation of AEs.

All safety data collected on or after the first dose of study drug administration up to 30 days after the last dose of study drug, unless specified otherwise, will be summarized by treatment group according to the study drug received.

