#### **8.5.6. Adverse Events**

Clinical and laboratory AEs will be coded using the Medical Dictionary for Regulatory Activities (MedDRA). System Organ Class, High-Level Group Term (HLGT), High-Level Term (HLT), PT, and Lower Level Term (LLT) will be attached to the clinical database.

TEAEs are:

- Any AEs with an onset date of on or after the study drug start date and no later than 30 days after permanent discontinuation of study drug or

- Any AEs leading to premature discontinuation of study drug.

Summaries (number and percentage of subjects) of TEAEs by system organ class and PT will be provided by treatment group. TEAEs will also be summarized by relationship to study drug and severity. In addition, TEAEs leading to premature discontinuation of study drug will be summarized and listed.

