3.7. Analysis Visit Windows

3.7.1. Definition of Study Day

The First Dosing Date of Double-Blind Filgotinib/Placebo is defined as the date when subjects take their first dose of double-blind filgotinib/placebo as recorded on the Study Drug Administration eCRF.

The Last Dosing Date of Double-Blind Filgotinib/Placebo is defined as the date when subjects take their last dose of double-blind filgotinib/placebo as recorded in the Study Drug Administration eCRF.

The Last Dosing Date of Any Filgotinib is defined as the date when a subject takes their last dose of double-blind or open-label filgotinib as recorded in the Study Drug Administration eCRF.

The Start Date of Extension Phase is defined as the first dose date of open-label filgotinib (for rheumatic disease responders randomized to filgotinib who continued on open-label filgotinib in extension phase) from the study drug administration eCRF or last dose date of double-blind study drug +1 day for subjects who have a non-missing standard of care start date in the extension phase of the study. In some countries, it takes time to obtain a new standard of care drug for rheumatic disease when subjects undergo a medication switch (especially for biologics), so the “standard of care” is to continue background medications alone or in rare cases, to take no rheumatic disease medication until the new regimen is available.

The End Date of Extension Phase is defined as last dose date of open-label filgotinib as recorded on the Study Drug Administration eCRF for subjects on open-label filgotinib in the Extension Phase. The end date for standard of care in extension phase will be 1 day prior to the date the subject went into the Monitoring Phase (ie, date the site was notified of subject meeting a prespecified sperm decrease threshold). Subjects who do not participate in Monitoring Phase but have a Study Completion eCRF that states that the subject has either completed study or prematurely discontinued study will have the last date of standard of care estimated using the last of the following dates: last Covance lab date, last eCRF visit date, date of last sperm sample collection, and death date (if subject died).

Study Day will be calculated from the first dosing date of double-blind filgotinib/placebo and derived as follows:

- For postdose study days: Assessment Date – On-Filgotinib/Placebo Study Day 1 + 1
- For days prior to the first dose: Assessment Date – On-Filgotinib/Placebo Study Day 1

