8.1.5. Treatment-Emergent Adverse Events

8.1.5.1. Definition of Treatment-Emergent Adverse Events

Treatment-emergent adverse events (TEAEs) during the double-blind phase are defined as 1 or both of the following:

- Any AEs with an onset date on or after the double-blind study drug start date through first dose date of open-label filgotinib/start date in extension phase minus 1 day (if subject enrolled in extension phase) or to last dose date of double-blind study drug + 30 days for subjects who permanently discontinue double-blind drug and do not enroll into extension phase (including subjects who meet a sperm decrease threshold who stop study drug and continue to be followed in the monitoring phase for reversibility)
- Any AEs leading to premature discontinuation of double-blind study drug

Treatment-emergent adverse events (TEAEs) during the extension phase are defined as 1 or both of the following:

- Any AEs with an onset date on or after first dose date of open-label filgotinib/first dose date in extension phase to last dose date of open-label filgotinib + 30 days for subjects who permanently discontinue open-label filgotinib (including subjects who meet a sperm decrease threshold who stop study drug and continue to be followed in the monitoring phase for reversibility) or all AEs for subjects who are ongoing on open-label filgotinib/standard of care in extension phase at the time of an interim analysis
- Any AEs leading to premature discontinuation of open-label filgotinib study drug

For example, for a subject who took double-blind placebo and switched to standard of care in the extension phase, TEAEs with an onset date on/after first dose date of double-blind filgotinib and prior to first date in extension phase will be TE for double-blind filgotinib (summarized with double-blind phase); from first date in extension phase up to last dose date of standard of care in extension phase + 30 days will be TE for standard of care (summarized by treatment sequence [double-blind filgotinib to standard of care] for the extension phase).

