For the overall study, the number of subjects with TE AEIs and SAEs, the corresponding PYE, the calculated EAIR, and the exact 95% CIs (defined in Section 8.1.5.3) will be summarized for each treatment (filgotinib and placebo) by PT for each AEI category and separately for SAEs. Filgotinib group will include filgotinib to open-label filgotinib treatment sequence plus the filgotinib exposure for filgotinib to SOC treatment sequence and those randomized to filgotinib who did not continue to extension phase. Placebo will include the placebo to SOC treatment sequence and those randomized to placebo who did not continue to extension phase.

Data listings for each AEI will also be provided.

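### In the overall-study incidence rates, SAP 8.1.5.3 gives filgotinib men switched to Standard of Care no post-dose window, against 30 days for the other two filgotinib subgroups and in the protocol

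*SAP*

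**What the plan says.** **Protocol.** Section 8.5.6 makes an adverse event treatment-emergent if its onset is "no later than 30 days after permanent discontinuation of study drug". Section 8.5.4 summarises safety data "up to 30 days after the last dose of study drug" by the study drug received, unless specified otherwise. Standard of Care is not study drug: "Study drug is defined as blinded filgotinib or placebo during the Double-blind Treatment Phase and open-label filgotinib during the Extension Phase" (Definition of Terms). Under Section 3.1, arthritis non-responders without a sperm decrease stop blinded drug at Week 13, start Standard of Care and have a safety visit 30 days after their last dose.

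**SAP, double-blind phase.** For men moved to Standard of Care, Section 3.7.1 starts the extension at "last dose date of double-blind study drug +1 day for subjects who have a non-missing standard of care start date". Section 8.1.5.1 runs double-blind treatment-emergent events "through first dose date of open-label filgotinib/start date in extension phase minus 1 day". The double-blind rate in Section 8.1.5.3 uses the earliest of "last dosing date of double blind phase +30, first date in extension phase of the study -1 day, death date, cutoff date".

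**SAP, overall study.** The same section lists the end dates for the whole-study rates of adverse events of interest and serious adverse events:
- Open-label filgotinib, permanently stopped: last dose plus 30 days.
- Men who never started the extension: last double-blind dose plus 30 days.
- Filgotinib switched to Standard of Care: "last dosing date of double-blind filgotinib [subjects in the filgotinib to standard of care group", with no addition.

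Section 8.1.7 builds the filgotinib column from the open-label sequence, "plus the filgotinib exposure for filgotinib to SOC treatment sequence", and men randomised to filgotinib who did not continue. The placebo column holds placebo men only.

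**The concern.** Within one list of end dates, one of three filgotinib subgroups is treated differently, and no reason is given. A man stopped for a sperm decrease at Week 13 goes to the Monitoring Phase, so his first 30 days off drug count towards filgotinib. A non-responder who stops the same drug at the same visit contributes nothing after his last dose. Whether early post-dose time counts therefore depends on arthritis response and next phase, not on drug exposure.

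The affected display covers serious infections, thromboembolic events and other serious adverse events. These may be few, so a single event can move a rate visibly. The difference does not come from comparing document versions: the SAP is based on Amendment 1, and the Amendment 2 summary of changes does not list Protocol 8.5.4 or 8.5.6.

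**Working it through.** The documents give no figure to reproduce, so the check applies the date rules and then sizes the gap.

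**1. End dates.** Let first dose be day 1 and last blinded dose day L.
- Extension start for a Standard of Care switcher = L + 1 (SAP 3.7.1).
- Double-blind end = min(L + 30, (L + 1) - 1) = L. The 30-day term never operates for these men.
- Overall-study end = L (SAP 8.1.5.3).
- Protocol treatment-emergent end = L + 30 (Protocol 8.5.6).

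**2. Per affected man.** With L = 91 (13 weeks), event-free time is 91/365.25 = 0.249 patient-years under the SAP and 121/365.25 = 0.331 under the protocol window. The share omitted is 30/121 = 24.8%. Blinded dosing continues until the Week 13 assessments are complete (Protocol 6.4), so L may be larger: 30/126 = 23.8% at L = 96, and 30/142 = 21.1% at L = 112.

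**3. Share of overall-study filgotinib time.** The non-responder share f is not given; assume 20% to 40%. Assume that all other filgotinib men continue on open-label drug. Days per randomised filgotinib man, with the 30 days restored:

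| f | Restored days (30f) | Week 26 cut (day 182) | Week 156 + 30 days (1092 + 30 = 1122) |
|---|---|---|---|
| 20% | 6 | 0.2×121 + 0.8×182 = 169.8; 6/169.8 = 3.5% | 0.2×121 + 0.8×1122 = 921.8; 6/921.8 = 0.7% |
| 40% | 12 | 0.4×121 + 0.6×182 = 157.6; 12/157.6 = 7.6% | 0.4×121 + 0.6×1122 = 721.6; 12/721.6 = 1.7% |

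**4. What happens to an event on post-dose day 10.** The listed end dates set person-time for men without an event; no sentence says which events enter the overall-study numerator. There are two readings:
- Section 8.1.7 admits only the filgotinib exposure of this sequence, so the event is outside the filgotinib column. The placebo column does not include the sequence. The event then enters neither rate.
- The event is kept in the filgotinib numerator. Section 8.1.5.3 then runs that man's time to his event, beyond L, while event-free men are cut at L. Men with events have a longer risk window than men without.

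The first reading fits the text better. The second is also inconsistent.

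**5. Direction.** Assume 125 filgotinib men, 38 of them such non-responders, the other 87 on open-label drug, a Week 26 cut, and 2 men with an event. For simplicity, ignore the shortening of person-time at an event.
- SAP rule: (38×91 + 87×182)/365.25 = 52.82 patient-years; 2/52.82 = 3.79 per 100.
- Restored time: 38×30/365.25 = 3.12 patient-years, total 55.94.
- No further man with an event: 2/55.94 = 3.58 per 100. One further man: 3/55.94 = 5.36 per 100.

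Restoring the window can lower or raise the rate.

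**The case against.** The strongest reply is that little is hidden. From the first extension day, SAP 8 and 8.1.5 treat these events as treatment-emergent. SAP 8.1.6 tabulates them by sequence, and the label double-blind filgotinib to Standard of Care keeps their origin visible. Serious events, deaths and each category of interest are also listed by subject. This stands: a reader who infers that the events vanish from the report would be wrong.

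A reader might also infer that the rule flatters filgotinib. The documents do not support that, because events and person-time are cut together (step 5).

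A third inference is that the arm comparison is biased. The between-group rate difference is planned for the double-blind phase only (SAP 8.1.7), where switchers from both arms are cut at the same point. The overall-study display has no planned difference.

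A fourth is that filgotinib loses 6-12% of its window: 6/97 = 6.2% to 12/103 = 11.7%. That divides by a Week 13 base, whereas the affected rate includes open-label exposure up to Week 156.

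Attribution after a switch is also partly a choice. Men may start a biologic, so early infections are confounded. But SAP 3.7.1 acknowledges that the new drug may take time to obtain, so some of these days carry background medication alone or, rarely, no rheumatic medication. Protocol 8.5.4 has its exception clause; the treatment-emergent definition in 8.5.6 does not. Neither document explains why one filgotinib subgroup differs from the other two. SAP 6.7 is silent here, but its title covers semen and hormone analyses only, so its silence shows little.

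**Conclusion.** The inconsistency is real and narrow. In the overall-study rates for adverse events of interest and serious adverse events, filgotinib men switched to Standard of Care have a post-dose window of zero days. The other two filgotinib subgroups and Protocol 8.5.6 use 30. This follows from the date rules as written and can be held with high confidence.

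That such events enter neither overall-study rate is an inference from SAP 8.1.7, held with moderate confidence; the alternative reading also needs correction.

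The assumption-free size, given 91 days of dosing, is 25% of each affected man's protocol window. The overall share depends on the assumed 20-40% and on everyone else continuing open-label: about 3.5-7.6% at a Week 26 cut, and about 0.7-1.7% with follow-up to Week 156 plus 30 days. No direction of bias is established. The change is worth making because it is cheap and the event types matter.

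**What to change.** - In SAP 8.1.5.3, set the overall-study end date for the filgotinib-to-Standard-of-Care group to the last double-blind filgotinib dose plus 30 days, or earlier death or data cutoff.
- State that adverse events of interest and serious adverse events with onset in that window count in the filgotinib column.
- In the extension-phase adverse-event tables, flag events within 30 days of the last blinded dose.
- Leave the double-blind comparison cut at the switch, so the arms stay symmetric.
- Record the change in the clinical study report, as SAP Section 1 requires for changes after finalisation.

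The cost is SAP wording, one date derivation and a flag; Protocol 3.1 already schedules the 30-day visit for these men. The downside is that an early event caused by newly started Standard of Care may be counted against filgotinib. The flag lets a reader see which events are open to that doubt.

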8. SAFETY ANALYSES

Safety analyses will be conducted on the Safety Analysis Set and Extension Phase Safety Analysis Set, defined in Section 3.1.3.

Safety data during the double-blind phase will be summarized based on actual treatment while the subject is on double-blind study drug. Subjects will be included in analysis after first dose date of double-blind study drug up to:

- First dose date of open-label filgotinib or first date in extension phase (minus 1 day for adverse events) for subjects who receive open label filgotinib or standard of care in extension phase
- Last dose date of double-blind study drug + 30 days (subjects meeting pre-specified sperm decrease thresholds at/prior to Week 13 who were switched to Monitoring Phase to assess reversibility of all sperm parameters meeting decrease thresholds; subjects permanently discontinued from study drug at/prior to Week 13)

Safety data during the extension phase will be summarized based on actual treatment sequence as described in Section 3.2 of this SAP. Safety data collected on (AEs only) or after first dose date of open-label filgotinib/first date in extension phase to:

- Last dose date of open-label filgotinib/standard of care in extension phase + 30 days will be included for subjects who have stopped or completed all study drug/SOC in the extension phase
- All available data (after start of extension phase) at time of data cut for subjects who are ongoing on open-label filgotinib/standard of care in the extension phase at the time of an interim analysis

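### SAP 8.1.5.3 gives placebo-to-Standard-of-Care men who complete Week 156 no Standard of Care end date, so their person-time in the overall-study rates runs to data cutoff or is undefined

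*SAP*

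**What the plan says.** SAP 8.1.5.3 defines patient-years of exposure (PYE). For a man with an event, PYE stops at event onset. "For subjects with no event", PYE runs to a calculation end date. For the overall-study display the rule opens "where calculation end date for the entire study display = the earliest date among" and then lists dates, most of them restricted in brackets to a group of subjects:

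- "last dosing date of OL filgotinib+ 30 days [subjects in the filgotinib to OL filgotinib sequence who permanently discontinued OL filgotinib"
- for men who moved from filgotinib to Standard of Care, their final double-blind dose
- "last date on standard of care in extension phase [subjects in placebo to standard of care sequence who switched to monitoring phase or early terminated" (once in the extension)
- "last dosing date of double-blind study drug + 30 for subjects who did not start extension phase, data cutoff date, death date"

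SAP 8.1.7 applies this to the overall-study rates of adverse events of interest and serious adverse events. It composes the comparator column as follows: "Placebo will include the placebo to SOC treatment sequence and those randomized to placebo who did not continue to extension phase".

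Two other places do name completers. SAP 3.7.1, defining the End Date of Extension Phase, covers "Subjects who do not participate in Monitoring Phase but have a Study Completion eCRF that states that the subject has either completed study" or was stopped early, and takes the latest of the last laboratory, visit, semen sample and death dates. SAP 8 sets a safety data window that "will be included for subjects who have stopped or completed all study drug/SOC in the extension phase".

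**The concern.** Finishing Week 156 on Standard of Care is the planned path for every placebo man who enters the extension and never meets a sperm threshold. If the exposure rule has no end date for him, the fallback is the data cutoff. Time between his last visit and that cutoff enters the denominator although nobody is collecting his adverse events, so it can only lower the rate. The display concerned gives the long-term rates of infections, malignancies, thromboembolic events and serious adverse events, with filgotinib and placebo shown together. A placebo rate that is too low makes filgotinib look worse for a reason that has nothing to do with safety.

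**Working it through.** The documents give no overall-study EAIR, PYE or event count, so there is no planned figure to reproduce. The check is of the rule, followed by arithmetic on its consequence.

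**1. Each listed term, tested on a placebo man who completes Week 156 on Standard of Care without Monitoring**

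| Term in the list | Applies? |
|---|---|
| Last open-label filgotinib dose + 30 days | No, he never took it |
| Last double-blind filgotinib dose | No, he was on placebo |
| Last Standard of Care date | No, he neither entered Monitoring nor terminated early |
| Last double-blind dose + 30 days | No, he started the extension |
| Data cutoff date | Yes |
| Death date | Only if he died |

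He cannot be read in as an early terminator: the programming note on disposition in SAP 4.1 classes a Standard of Care man who finishes without Monitoring as having completed the extension. A man who meets a sperm threshold at Week 156 does enter Monitoring, so the bracket covers him.

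**2. Can the added time contain events?** Protocol 7.3 collects adverse events until the last study visit, and Protocol 3.8 allows that visit to be Week 156. His last study drug dose was at about Week 13, so the 30-day post-dose reporting period for serious events is long past. The added time has no systematic event collection.

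**3. One event-free completer.** PYE = (end date − first date + 1)/365.25. With the Section 3.7.1 date, 1092/365.25 = 2.99 years. Under the literal rule he contributes 2.99 + g, where g is the assumed number of years from last visit to cutoff.

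| g (years) | Literal PYE | Correct/literal |
|---|---|---|
| 0 | 2.99 | 1.00 |
| 0.25 | 3.24 | 0.92 |
| 0.5 | 3.49 | 0.86 |
| 1 | 3.99 | 0.75 |
| 2 | 4.99 | 0.60 |

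**4. The whole sequence.** All inputs here are assumptions: uniform accrual over 6 to 18 months; cutoff 0 to 52 weeks after the last Week 156 visit; share p = 40% to 80% completing; the rest leaving uniformly between days 182 and 1092, mean (182 + 1092)/2 = 637 days. The mean gap G is half the accrual period plus the lag to cutoff, and

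inflation = 1 + pG / [1092p + 637(1 − p)].

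- Mildest: 6 months, no lag, p = 0.4. G = 91.3; 1 + 36.5/819 = 1.045; rate 4% too low.
- Middle: 12 months, 26 weeks, p = 0.6. G = 182.6 + 182 = 364.6; 1 + 218.8/910 = 1.240; rate 19% too low.
- Largest: 18 months, 52 weeks, p = 0.8. G = 273.9 + 364 = 637.9; 1 + 510.3/1001 = 1.510; rate 34% too low.

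This treats all completers as event-free. Men with an event stop at onset and are not inflated. The placebo column also includes men who never entered the extension, which dilutes the effect.

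**5. A second set-up, in EAIR units.** Assume 100 placebo men, 5 events, half of the men completing and the others averaging 1 year. Correct PYE = 50 × 2.99 + 50 × 1 = 199.5, EAIR 2.51 per 100 PYE. With g = 0.25, 1 and 2 years, PYE becomes 212.0, 249.5 and 299.5 and EAIR 2.36, 2.00 and 1.67, that is 6%, 20% and 33% too low.

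**6. Which analyses are exposed.** Protocol version 1.0 is dated 05-Feb-2019; adding 1092 days gives 01-Feb-2022 as the earliest possible completion. The SAP was signed in January 2021, so a first interim analysis near that date has no completers. The protocol says that the data monitoring committee had already covered the second interim data by Amendment 2 (09-Sep-2022). The gap by that date is at most 220 days (0.60 years), and only for a man randomised on the date of protocol version 1.0. The final analysis (SAP 2.5) waits for every subject, including up to 52 weeks of Monitoring that can begin at Week 156, so early completers may by then have left long before.

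**The case against.** The strongest reply is that the SAP mentions data cutoffs mainly in connection with interim analyses (SAP 4.1, 4.2.1, 6.6.2 and 8), while SAP 2.5 names none for the final analysis. The likelier result there is an undefined end date, which a programmer would have to resolve and could resolve correctly with the Section 3.7.1 date. That stands as a limit on the consequence. It does not close the gap, because the written rule does not point to that date.

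A reader might infer that the error is one-sided against placebo. The documents do not establish this. The open-label filgotinib bracket is limited to men who permanently discontinued, and 8.1.5.3 does not say that finishing at Week 156 counts. SAP 3.7.1 supports that reading, since it describes the first follow-up day as the one after permanent discontinuation of all study drugs. SAP 8, however, names stopping and completing separately. If both brackets are read strictly, open-label completers have the same gap.

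A reader might also take 4% to 34% as an estimate for this trial. It is not: accrual, completion, dropout pattern and cutoff are all assumed.

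Finally, the overall-study display plans rates and intervals by treatment but no between-group difference. The difference is planned only for the double-blind phase, where the end date is capped the day before the extension starts. If the bias arises only in the placebo column, it makes filgotinib look worse and so does not conceal a risk.

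**Conclusion.** The omission is real. The written rule leaves a placebo-to-Standard-of-Care completer with only data cutoff or death. Where a cutoff later than his last visit is applied, the overall-study placebo EAIR is understated; where none is set, his end date is undefined. The direction for the placebo column follows from the formula and needs no assumption beyond a positive gap. The size cannot be derived from the documents: zero when cutoff and last visit coincide, increasing with the gap, and illustratively about 4% to 34% for the sequence under the stated assumptions. The effect is confined to event-free completers and falls mainly on the final analysis. The double-blind EAIR and its between-group difference are untouched. Whether the filgotinib column is also affected depends on how permanent discontinuation of open-label drug is read.

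**What to change.** Three changes to SAP 8.1.5.3:

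1. In the placebo-to-Standard-of-Care bracket, add *or completed the study*, and identify the date as the End Date of Extension Phase in Section 3.7.1.
2. State that permanent discontinuation of open-label filgotinib includes subjects who completed Week 156.
3. Keep the data cutoff date and the death date as caps for all subjects.

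The third item matters. Restricting the cutoff to subjects still in the extension would let the terms with 30 added days run past an interim cutoff for men who stopped drug shortly before it; the present list prevents that.

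The cost is a sentence or two of text and a small programming change, using a date the SAP already derives. No new data are needed. SAP 1 provides for changes after finalisation to be documented in the clinical study report.
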